12.3.10. Treatment Period Days 8-13

- AEs
- Concomitant medications
- Survival status
- For all subjects, a cohort-specific veledimex dose
- Complete veledimex dose diary
- Patient contact to discuss clinical status and updates on current/new adverse events.
- PI/MM contact regarding clinical status and laboratory values, prior to veledimex administration

12.3.11. Treatment Period Day 14

- Physical examination (including targeted neurological examination)
- Lansky Performance Status, Karnofsky Performance Status, or ECOG status

- Weight
- Vital signs
- AEs
- Concomitant medications
- Survival status
- **Hematology Panel including:** CBC, including WBC count with differential, RBC count, hematocrit, hemoglobin and platelet count, and ESR
- **Coagulation Panel including:** aPTT/PTT and INR
- **Serum Chemistry Panel including:** AST, ALT, LDH, ALP, lipase, amylase, creatinine, total bilirubin, total protein, albumin, BUN, glucose, sodium, potassium, chloride, calcium, phosphorus, CRP, and bicarbonate
- **Urinalysis Panel (dipstick) including:** appearance, pH, specific gravity, glucose, protein/albumin, presence of blood, ketones, bilirubin, nitrates, and leukocyte esterase. In addition, a microscopic exam for casts, crystals, and cells may be done if clinically indicated
- ECG
- For all subjects, a cohort-specific veledimex doseComplete veledimex dose diary
- [REDACTED]
- Blood sample for veledimex PK (Arm 1: [Table 2](#); Arm 2: [Table 3](#))
- [REDACTED]
- [REDACTED]
- MRI scan. CSF may be collected at time of MRI via Ommaya reservoir. Collection is optional.
- Patient contact to discuss clinical status and updates on current/new adverse events.
- PI/MM contact regarding clinical status and laboratory values, prior to veledimex administration
- [REDACTED]

12.3.12. Initial Follow-Up Period Day 15

- AEs
- Concomitant medications
- Survival status
- Blood sample for veledimex PK (Arm 1: [Table 2](#); Arm 2: [Table 3](#))

12.3.13. Initial Follow-Up Period Day 28 (± 7 days)

- Physical examination (including targeted neurological examination)
- Lansky Performance Status, Karnofsky Performance Status, or ECOG status
- Weight
- Vital signs
- AEs
- Concomitant medications
- Survival status
- **Hematology Panel including:** CBC, including WBC count with differential, RBC count, hematocrit, hemoglobin and platelet count, and ESR
- **Serum Chemistry Panel including:** AST, ALT, LDH, ALP, lipase, amylase, creatinine, total bilirubin, total protein, albumin, BUN, glucose, sodium, potassium, chloride, calcium, phosphorus, and bicarbonate
- Urine or serum pregnancy test for females of childbearing potential

■ [REDACTED]
■ [REDACTED]
■ [REDACTED]

- MRI scan. CSF may be collected at time of MRI via Ommaya reservoir. Collection is optional.

■ [REDACTED]

12.3.14. Initial Follow-Up Period Day 56 (± 7 days)

- AEs
- Concomitant medications
- Survival status
- MRI scan. CSF may be collected at time of MRI via Ommaya reservoir. Collection is optional.
- **Arm 2:** A tumor sample should be collected once there is a concern of pseudo-progression. The biopsy at Day 56 is strongly recommended. Patients should remain on-study for continued follow-up until confirmed progression per iRANO or the patient meets other withdrawal criteria.

■ [REDACTED]

12.3.15. Long-Term Follow-Up (every 8 weeks ± 1 week)

- Concomitant medications (subjects will be followed to document start of new anticancer treatments and survival status for two years following administration of Ad-RTS-hIL-12, [Day 0])
- MRI scan. CSF may be collected at time of MRI via Ommaya reservoir. Collection is optional.

■ [REDACTED]

12.3.16. Unscheduled Visit Collections

In the event of subject termination or an unscheduled visit for a drug-related AE, an unscheduled visit kit should be obtained [REDACTED] for CSF evaluation, if applicable.

■ [REDACTED]

- A tumor sample should be collected if there is a concern of pseudo-progression. The biopsy at Day 56 is strongly recommended. Patients should remain on-study for continued follow-up until confirmed progression per iRANO or the patient meets other withdrawal criteria.
- CSF may be collected at time of the time of MRI scans such as if sedation is clinically indicated or if an Ommaya reservoir is implanted. Collection is optional.

13. TUMOR RESPONSE ASSESSMENTS

13.1. Tumor Response

The secondary time-to-event endpoints of this study include Investigator assessment of ORR, PFS, and OS.

Tumor response will be evaluated radiographically using MRI scans to determine tumor response and to assess the time of objective disease progression (estimate of PFS). A baseline MRI will be performed on Day 2 (a window of \pm 24 hours is allowed). The Ad-RTS-hIL-12-injected lesion and/or other measurable brain lesions will be measured according to the iRANO criteria guidelines for adults, pending issuance of pediatric criteria ([Okada, Weller et al. 2015](#)) (see [Appendix 6](#)). MRI scans will be collected and stored at the study site and each subject will be evaluated for response by the study Investigator. MRI scans and reports should be sent to the Sponsor per the Sponsor's defined process. Subjects should be imaged throughout the study using the same method(s) as were used for the screening and baseline MRIs. Independent tumor response assessments, as well as posttreatment tumor biopsies, may occur as available and at the discretion of the Investigator. A tumor sample should be collected if there is a concern of pseudo-progression. The biopsy at Day 56 is strongly recommended. Repeat scans to confirm progression should be completed at 4 weeks and preferably again at 12 weeks (per iRANO) after first documentation of progression, if within 6 months of starting investigational therapy. Consideration should be given to performing a diagnostic brain biopsy, which should be performed in accordance with the current iRANO guidelines.

Response is defined by radiographic and clinical criteria. Complete response (CR) or partial response (PR) will be first assessed by radiographic changes that indicate a reduction of bidimensional tumor size as per iRANO criteria. In addition, changes in neurologic function and steroid use will be considered to determine stable disease.

Tumor response assessments will occur at Day 14, at 4 weeks (Day 28 \pm 7 days), at 8 weeks (Day 56 \pm 7 days), and every 8 weeks (\pm 7 days) thereafter for all subjects, including those who may have experienced a dose delay or missed a dose, until the occurrence of confirmed tumor progression, initiation of alternative therapy, or two years following administration of Ad-RTS-hIL-12 (Day 0), whichever occurs first.

13.2. Tumor Response Evaluation and Pseudo-Progression

The interpretation of MRI findings in subjects with treated brain tumors has an inherent uncertainty that stems from the pseudo-progression phenomena. Pseudo-progression is a term used to describe the appearance of radiographic disease progression due to increase contrast enhancement on MRI without true tumor progression. The increase in contrast enhancement can be influenced by several parameters including differences in radiologic technique, the amount of contrast agent used, the timing of the contrast agent administration relative to the imaging, postsurgical changes, infarction, treated related inflammation, seizure activity, sub-acute radiation effects, radiation necrosis, and corticosteroid use. Consideration of these factors by experts and clinical experience is likely to identify these subjects. In this study, pseudo-progression is unlikely to impact the duration of Ad-RTS-hIL-12 + veledimex therapy since the veledimex treatment period lasts 14 (Arm 2) to 15 (Arm 1) days. Imaging assessments

will be performed using iRANO criteria. A tumor sample should be collected once there is a concern for pseudo-progression as noted above. The biopsy at Day 56 is strongly recommended. Patients should remain on-study for continued follow-up until confirmed progression per iRANO or the patient meets other withdrawal criteria.

14. ASSESSMENT OF SAFETY

Safety will be evaluated in the Overall Safety Population (OSP) and the Evaluable Safety Population (ESP) using CTCAE v5.0.

The OSP includes all subjects who received at least 1 dose of veledimex or Ad-RTS-hIL-12.

The ESP includes all subjects who received Ad-RTS-hIL-12 and at least one dose of veledimex after Ad-RTS-hIL-12 administration, and are BSA conformant.

14.1. Adverse Events and Definitions

Adverse Event

Any untoward medical occurrence associated with the use of a drug in humans, whether or not considered drug-related. An AE can be any unfavorable and unintended sign including an abnormal laboratory finding, symptom, disease temporarily associated with the use of a medical treatment or procedure, and any worsening of a pre-existing condition regardless of causality to study drug. An AE is also known as an adverse experience.

Suspected Adverse Reaction

Any AE for which there is evidence to suggest a causal relationship (reasonable possibility) between the drug and the AE. A suspected adverse reaction implies a lesser degree of certainty about causality than an adverse reaction.

Adverse Reaction

Any AE caused by the use of a drug. Adverse reactions are a subset of all suspected adverse reactions for which there is reason to conclude that the drug caused the event.

Unexpected Adverse Reaction

Any AE that is (a) not listed as an adverse drug reaction in the Investigator's Brochure, (b) not listed with the specificity and severity that is being observed, (c) not consistent with the risk information described in the general investigational plan or elsewhere in the current application (in the absence of an Investigator Brochure), and (d) listed as occurring with a class of drugs, but not specifically mentioned as occurring with the particular drug under investigation.

14.2. Evaluation of Adverse Events

Adverse events include:

- Suspected adverse drug reactions
- Reactions from study drug overdose, abuse, withdrawal, sensitivity, or toxicity
- Significant changes or abnormalities, when compared to baseline, in signs, symptoms, clinical laboratory results, or physiological testing. This includes any worsening of a pre-existing condition temporally associated with the use of study drug.
- Other untoward medical events, regardless of their relationship to the study drug, such as injury, events that require surgery, accidents, extensions of symptoms, or apparently unrelated illnesses.

The following considerations apply when identifying an AE:

- Anticipated day to day fluctuations of pre-existing conditions, including the disease under study, that do not represent a clinically significant exacerbation or worsening need not be considered AEs.
- In the event that a constellation of symptoms results in a confirmed diagnosis, the diagnosis (not the symptoms) should be recorded as the AE term.
- If a diagnosis cannot be established, the symptoms should be recorded as the AEs.
- If an ongoing symptom has been included in the medical history, an associated severity grade and frequency should also be documented so that a worsening in severity or frequency of a symptom can be readily identified as an AE.
- Progression of disease is not itself an AE; however, the presenting sign or symptom of the disease progression should be documented as an AE (e.g., increase in pain). However, if a subject experiences progression of disease that results in death, “progression of disease” should be reported as an SAE if, by medical opinion, the term best describes the cause of death.

Adverse events will be recorded from the time of consent and followed through the initial follow-up period (Day 56). AEs that are ongoing at Day 56 and considered drug related should be followed until resolved or no resolution is expected.

14.3. Determination of Seriousness

14.3.1. Serious Adverse Event

An AE is considered an SAE if at least one of the following conditions applies:

- Death: An AE that results in death during the active study period or within 30 days following study drug administration. In addition, a reported death at any time post study that is thought to be related to study drug administration.
- Life-threatening AE: An AE that places the subject, in the view of the Investigator, at immediate risk of death from the event as it occurred (i.e., this does not include a reaction that, had it occurred in a more severe form, might have caused death).
- Permanent, persistent, or significant disability: A disability is defined as any substantial disruption of a person’s ability to conduct normal life functions.
- Inpatient hospitalization or prolongation of existing hospitalization: In general, hospitalization refers to admission of a subject into a hospital for at least a 24-hour stay. Hospitalizations for routine blood transfusions, hospitalization for an elective or diagnostic procedure, or surgery for a pre-existing condition that has not worsened, are not considered SAEs. Emergency room visits that do not result with admission are not considered as SAEs.
- A congenital anomaly/birth defect: A fixed, permanent impairment established at or before birth.

- Important medical event: Events that may not result in death, be life-threatening, or require hospitalization may be considered SAEs when, based upon appropriate medical judgment, they jeopardize the subject and require medical or surgical intervention to prevent a life-threatening- situation, hospitalization, or death. Important medical events also include:
 - New cancer: Occurrence or diagnosis of a new cancer during the trial is considered an SAE (this does not pertain to metastasis of current disease);
 - Any AE associated with an overdose of the study drug: An overdose of study drug is defined as an occurrence of administered dose exceeding that which is prescribed by the Investigator per protocol.

14.3.2. Non-Serious Adverse Event

An AE that does not fulfill the criteria for a SAE is classified as a non-serious AE.

14.4. Determination of Severity

The severity of AEs will be assessed according to the NCI CTCAE, v.5.0. If the AE is not defined in the NCI CTCAE, v.5.0, the Investigator will determine the severity of an AE based on the following definitions:

- Mild (Grade 1): The AE is noticeable to the subject but does not interfere with routine activity. The AE does not require discontinuing administration or reducing the dose of the study drug.
- Moderate (Grade 2): The AE interferes with routine activity but responds to symptomatic therapy or rest. The AE may require reducing the dose, but not discontinuation of administration of the study drug.
- Severe (Grade 3): The AE significantly limits the subject's ability to perform routine activities despite symptomatic therapy. In addition, the AE leads to discontinuation of administration or reducing the dose of the study drug.
- Life-threatening (Grade 4): The AE requires discontinuing administration of the study drug. The subject is at immediate risk of death.
- Death (Grade 5): The subject dies as a direct result of the complication or condition.

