7.4. Dose-Limiting Toxicity

An event, occurring within the first 28 days (*i.e.*, Day 0 to Day 28) that meets at least one of the following conditions:

- Any local reaction that requires operative intervention and is felt to be attributable to study drug
- Any local reaction that has life-threatening consequences requiring urgent intervention or results in death and is felt to be attributable to study drug
- Any Grade 3 or higher non-hematologic adverse event that is at least possibly related to study drug and lasts ≥ 3 days
- Nausea and vomiting will not be considered a DLT unless at least Grade 3 or 4 and refractory to antiemetics (*i.e.*, defined as symptoms unrelieved by maximal medical support as directed by the PI (per institutional guidelines) in consultation with the medical monitor).
- Grade 3 or higher thrombocytopenia ($< 50,000/\text{mm}^3$) at least possibly related to study drug

- Any Grade 4 or higher hematologic toxicity (except thrombocytopenia) that is at least possibly related to study drug and lasts ≥ 5 days

Dose escalation may be stopped by the Medical Monitor before a DLT is observed, but where the observed toxicities indicate the strong likelihood of unacceptable toxicity at higher doses.

Note: Diagnostic brain tumor biopsy is not considered a DLT. Seizures, headaches, and cerebral or pontine edema are commonly observed in this population and will be recorded according to the grade of toxicity but will not be considered a DLT unless a relationship to study drug is deemed to be the main contributory factor. Transient neurological changes are expected in Arm 2 and will not be considered a DLT unless they last > 10 days.

Expansion cohorts will be allowed in Arm 2 if deemed appropriate by the SRC. If an expansion cohort is implemented, the veledimex dose may be delayed or reduced for individual subjects in the event of toxicity. If $\geq 33\%$ of subjects in the expansion cohort experience DLTs, using the definition in the dose-escalation phase, additional subjects may be enrolled at the next lower dose tested in the dose-escalation phase or at an intermediate dose, as recommended by the SRC. All DLTs should be reported to the Sponsor within 24 hours of Investigator/site awareness.

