7.6. Dose Modification and Dose Delays

Treatment dose delays and dose reductions for individual subjects will be allowed in the event of toxicities, according to the criteria shown in [Table 6](#). If a drug-related Grade 3 or higher AE occurs (excluding nausea and/or vomiting in subjects who did not receive optimal treatment with anti-emetics), the Investigator in conjunction with the Sponsor's Medical Monitor will decide whether the subject will remain on the study. The withheld doses will not be made up; the subject may be allowed to complete dosing according to the remaining schedule.

As mentioned in [Section 7.4](#), fatigue, seizures, headaches, and cerebral or pontine edema are commonly observed in this population and will be recorded according to grade of toxicity, but

will not be considered a DLT unless a relationship to study drug is deemed to be the main contributory factor. If $\geq 33\%$ of subjects experience DLTs, the SRC will convene to determine the course of action. The Medical Monitor or Investigators may request a meeting of the SRC at other times, as deemed clinically indicated.

Table 6: Criteria for Dose Delay and Dose Reduction

Event	Course of Action
Any local injection reaction that requires operative intervention	Hold study drug and contact the Medical Monitor for instructions on resuming dosing
Any local injection reaction that has life-threatening consequences requiring urgent intervention or results in death	Hold study drug and contact the Medical Monitor for instruction on resuming dosing
Any drug-related Grade 3 or higher AE ^a	Hold study drug and contact the Medical Monitor for instruction on resuming dosing

^a Excluding nausea and/or vomiting in subjects who did not receive optimal treatment with anti-emetics

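### For adverse events not defined in CTCAE, fallback Grade 3 depends on a study-drug action that is impossible after Day 14, so a severe event on Days 15 to 28 has no clear grade for the DLT rule

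*Protocol*

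**What the plan says.** Protocol 14.4 starts from the standard scale: "The severity of AEs will be assessed according to the NCI CTCAE, v.5.0". Only where CTCAE does not define the event does it turn to its own scale, under which "the Investigator will determine the severity of an AE based on the following definitions". The parts of that scale that matter here are:

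- **Grade 2:** "The AE interferes with routine activity but responds to symptomatic therapy or rest". A dose reduction is possible but not necessary.
- **Grade 3:** "The AE significantly limits the subject's ability to perform routine activities despite symptomatic therapy". A second sentence follows: "In addition, the AE leads to discontinuation of administration or reducing the dose of the study drug".
- **Grade 4:** "The AE requires discontinuing administration of the study drug", together with immediate risk of death.
- **Grade 5:** death, with no condition about study drug.

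Two rules read the grade. Protocol 7.4 counts as a DLT "Any Grade 3 or higher non-hematologic adverse event that is at least possibly related to study drug and lasts" 3 days or more. Table 6 in Protocol 7.6 says, for a drug-related event of Grade 3 or higher, "Hold study drug and contact the Medical Monitor for instruction on resuming dosing". The SAP (13.1) also tabulates treatment-emergent events of Grade 3 or higher.

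**The concern.** Severity and action taken with study drug are different measurements. Protocol 14.6 treats them so, recording severity, causality and action taken as separate items. The fallback scale in 14.4 merges two of them. That causes trouble where no action is possible, and where the action is itself decided from the grade.

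The primary endpoint is the AE rate and the occurrence of DLTs in each cohort (16.3.1). If a severe event cannot be given Grade 3, it drops out of the main non-hematologic DLT criterion and out of the tables of Grade 3 or higher. The error runs one way, towards counting less toxicity at a dose level. Under 7.3, one DLT among the first three subjects calls for three more, and one or more DLTs among those three stops dosing. A single event can therefore decide which branch is taken.

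**Working it through.** The plan gives no figure that depends on this definition, so there is none to reproduce. The check sets the definitions against the dosing calendar.

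**Inputs.** Last veledimex dose: Day 14 in Cohorts 1, 3 and 4 (Section 4, Dose Schedule). Vector: one administration, Day 0 (7.1). DLT window: Day 0 to Day 28 (7.1, 7.4). Decision rule: 3+3 (7.3, Table 5).

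**Step 1: grade a test event.** Take a non-fatal event not defined in CTCAE and not a local reaction. It starts on Day 20, limits routine activity despite treatment, is possibly related and lasts more than 3 days.

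- Grade 2 does not fit, because the event does not respond to therapy or rest.
- Grade 3 fits on clinical effect. The second condition is joined to the first as a further requirement, and with no dose left it cannot be met.
- Grade 4 applies only if there is immediate risk of death, and even then the wording about discontinuing is open to two readings.
- Grade 5 does not apply.

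No grade fits in full. Without Grade 3, the event does not meet the non-hematologic criterion in 7.4 as written.

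**Step 2: count the exposed days.** Days 15 to 28: 28 − 15 + 1 = 14. Days 0 to 28: 28 − 0 + 1 = 29. Share: 14/29 = 48% (or 14/28 = 50% counting from the day after injection).

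**Step 3: the dosing period.** Table 6 makes Grade 3 or higher the trigger for a hold. Section 14.4 makes discontinuation or reduction part of what defines Grade 3. For fallback-graded events each rule therefore waits on the other. A hold is also not plainly a discontinuation or a reduction, since 7.6 allows the subject to finish the remaining schedule. In addition, Table 6 acts only on drug-related events. A severe unrelated event that prompts no dose change fails fallback Grade 3, although treatment-emergent events are counted regardless of relationship (16.4.2).

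**Step 4: what missed DLTs do to a 3+3 cohort (illustration).** The documents give neither the DLT rate nor the share of DLTs that would be missed, so both are assumptions. With true rate p and missed share f, the counted rate is q = p(1 − f), and

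P(cohort passes) = (1 − q)³ + 3q(1 − q)² × (1 − q)³.

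For p = 0.33 and f = 0: 0.301 + 0.444 × 0.301 = 0.434. For f = 0.10, q = 0.297: 0.347 + 0.440 × 0.347 = 0.500.

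| True DLT rate | f = 0 | f = 5% | f = 10% | f = 25% |
|---|---|---|---|---|
| 20% | 0.709 | 0.730 | 0.752 | 0.814 |
| 33% | 0.434 | 0.467 | 0.500 | 0.605 |
| 50% | 0.172 | 0.202 | 0.234 | 0.351 |

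The columns with small f are the relevant ones, because the fallback covers only events outside CTCAE. The table shows direction and sensitivity. It does not estimate the effect in this trial.

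**The case against.** The strongest reply is that investigators will grade on clinical effect. They are told to determine severity, the clinical half of Grade 3 is the nearest match, and few events fall outside CTCAE. There are also safeguards that do not depend on the grade. The Medical Monitor may stop escalation before any DLT (7.4). The SRC weighs the 3+3 result with other clinical factors (16.2) and may recommend de-escalation at any point (7.3). Seriousness is judged separately (14.3), SAEs are reported within 24 hours through Day 56 (14.7), and the SAP lists events by subject, so a severe event stays visible. These safeguards limit the harm. They do not correct the grade, the DLT count or the tables. If investigators would disregard the clause anyway, it serves no purpose; if some of the approximately 3 to 5 centers apply it and others do not, grading differs by site.

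On circularity, withheld doses are not made up (7.6), so a hold lowers the total dose and could be called a reduction. That reading is possible, but 14.4 does not state it.

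A reader might infer that a severe event after Day 14 can never be a DLT. The documents do not support that. One criterion in 7.4 is enough, and two of them use no grade: an attributable local reaction that needs surgery, and one that is life-threatening or fatal. A fatal event can be Grade 5, which carries no drug-action condition. The Grade 4 wording can also be read as what the event would call for, in which case a life-threatening event on Day 20 is still Grade 4.

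A reader might also infer that such events are downgraded to Grade 2. Step 1 shows that Grade 2 does not fit either. The result is an event without a fitting grade, not a demonstrated downgrade.

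**Conclusion.** The point holds in a limited form, and the text should be changed. For events not defined in CTCAE, fallback Grade 3, and arguably Grade 4, depends on an action that is unavailable once dosing has ended. Non-fatal events that start on Days 15 to 28, other than qualifying local reactions, can therefore miss the non-hematologic DLT criterion on a literal reading. During dosing the same definition is circular with Table 6.

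This rests on reading the two Grade 3 sentences as jointly required, which is their plain sense. The exposed period is 48% of the calendar days in the DLT window. It would be wrong to take that as a share of events, because the documents say nothing about when events occur or how many lie outside CTCAE. The number affected is probably small. Its importance comes from cohorts of 3 to 6 subjects: one missed event can mean three further subjects are not enrolled (0 of 3 in place of 1 of 3), or that a cohort passes when dosing should have stopped (1 of 6 in place of 2 of 6). Not every count is sensitive in this way.

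A related uncertainty is that the SAP (13.1) grades by CTCAE v4.03 and gives no fallback definitions, while the protocol uses v5.0. Which events go to the fallback scale is therefore itself unsettled.

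**What to change.** In Protocol 14.4, remove the drug-action clauses from fallback Grades 3 and 4, so that severity rests on clinical effect alone. Remove them from Grades 1 and 2 as well for consistency; there they cause no gap, since one is met automatically after Day 14 and the other is only permissive. Keep action taken with study drug as the separate item under 14.6. Then reconcile 14.4 with 7.4 and Table 6, so that the grade is fixed before any rule acts on it, and have the SAP cite the same CTCAE version and fallback scale as the protocol.

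The cost is one clause per grade and a cross-reference. No data are lost and no procedure is added. The change concerns how severity is measured; it takes no position on when study drug should be held, reduced or stopped.
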